1.1.2. Study Objectives

This statistical analysis plan (SAP) is designed to outline the methods to be used in the analysis of study data to answer the study objectives. Populations for analysis, data handling rules, statistical methods, and formats for data presentation are provided. The statistical analyses and summary tabulations described in this SAP will provide the basis for the results sections of the clinical study report (CSR) for this trial. Any differences in the currently planned analytical objectives relative to those planned in the study protocol will also be outlined in this document.

1.1.2.1. Primary Objectives

There are three primary objectives for this trial:

- To evaluate the tolerability and safety of INO-4700 administered by ID injection, and followed by EP, in healthy adult volunteers
- To evaluate the cellular (T cell) and humoral immune responses to INO-4700 administered by ID injection followed by EP for identification and confirmation of an optimal dose and regimen
- To evaluate selected optimal dose for safety and immunogenicity

1.1.2.2. Exploratory Objectives

The exploratory objectives include the following:

- To evaluate the expanded immunological profile by assessing both T and B cell immune responses
- To evaluate the cellular (T cell) and humoral immune response to INO-4700 administered by ID injection followed by EP for impact of boosting with a third dose
- Evaluate humoral immune response cross reactivity to other coronaviruses

1.2. Study Design

1.2.1. Synopsis of Study Design

MERS-201 is a Phase 2a, randomized, blinded, placebo-controlled, multi-center trial, designed to evaluate the safety, tolerability, and immunological profile of INO-4700. The study drug will be administered by ID injection followed by EP using the CELLECTRA™ 2000 device in healthy adult volunteers. The primary objectives of this trial are to evaluate the tolerability, safety, and immunogenicity of INO-4700 administered by ID injection followed by EP in healthy adult volunteers according to the regimens outlined in [Table 1-1](#), [Table 1-2](#), [Table 1-3](#) and Figure 1 of the MERS-201 Protocol.

Approximately 542 healthy volunteers will be evaluated across two (2) parts of this study, Part 1 and Part 2. Participation is exclusive to Part 1 or Part 2; participants from Part 1 do not roll over to Part 2. INO-4700 or placebo (SSC-0001) will be administered ID in ~0.1 mL dose volume followed immediately by EP.

Part 1 – Dose Finding

In Part 1, approximately 192 participants ages 18-50 years will be assessed through five (5) dose levels and regimens. These five (5) dosage levels and regimens will be evaluated across nine (9) groups designated Study Groups A, B, C, D, E, F, G, H, and I.

- Study Groups A, B, C, D, and E will receive INO-4700 and enroll approximately 32 participants per group.
- Study Groups F, G, H, and I will receive placebo and enroll approximately 8 participants per group.

Following the Data Safety Monitoring Board (DSMB) evaluation and the completion of the Week 10 visit, Part 1 will be unblinded. The optimal regimen will be chosen based on optimal immune response, acceptable safety profile, and dose tolerance. Part 1 participants will be followed for the full 48 weeks, until the planned end of study visit.

Part 2 – Expansion

In Part 2A, approximately 350 participants will be evaluated across the one (1) dose level determined in Part 1. Enrollment into Part 2 may begin following completion of the Week 10 visit. Participants will be randomized to receive active treatment (n=300) or placebo (n=50).

In Part 2B, a booster dose will be administered to a subset of the participants from Part 2A. The first 200 participants from the Active treatment group will be randomized to receive either a booster dose or placebo at Week 48 (in addition to the first 2 doses at Day 0 and Week 4 or 8). Similarly, the first 25 participants from the Part 2A Placebo group will receive placebo at Week 48 as a control for Part 2B. All participants receiving a third dose at Week 48 (collectively 225 participants) will be followed for 68 weeks from the Day 0 dosing (i.e., Week 68 will be the planned End of Study [EOS] visit). These 225 patients will be enrolled first. The remaining 125 participants in Part 2A (i.e., those receiving only 2 doses) will be followed for 48 weeks from the Day 0 dosing (i.e., Week 48 will be the planned EOS visit).

1.2.2. Randomization Methodology

Part 1 of this study will be randomized across Study Groups A through I. Part 2 of this study will be randomized between the selected optimal active dose from Part 1 and placebo groups. The study is investigator-and-participant blinded except for the site pharmacy across all study groups for both parts of the study. The Sponsor will be blinded in Part 1 until Week 10 and blinded for the entire duration of Part 2 of the study.

Part 2 of the study includes an analysis at Week 12 to produce group-level, unblinded summaries of immunogenicity and safety. The first 225 subjects in Part 2 will be randomized to booster dose regimens and followed for 68 weeks; the remaining 125 subjects will be randomized to two dose regimens and followed for 48 weeks. The Sponsor will continue to remain blinded to subject-level treatment allocation for the remainder of the trial.

For details, see the randomization plan found in [Appendix B](#) of this SAP.

1.2.3. Stopping Rules and Unblinding

The trial will be stopped for any of the following criteria:

- Any treatment-related serious adverse event
- Any Grade 4 toxicities related to study treatment
- Any report of anaphylaxis from study treatment.

Should any of these criteria be met, at any time point in the study, the DSMB will be notified immediately. The study may be paused or stopped if the DSMB consider the safety data unsatisfactory. In this case, further enrollment of participants and further administration of INO-4700 or placebo to participants will be paused for further evaluation. An investigation will be undertaken by the Sponsor in consultation with the DSMB, and other experts if needed, to determine whether to resume randomization and/or dosing of the remainder of enrolled participants.

1.2.4. Study Procedures

The schedule of assessments, as outlined in the study protocol, are provided in

[Table 1-1, 1-2, and 1-3.](#)

Table 1-1 Part 1 Schedule of Assessments

Tests and assessments	Screen ^a	Day 0		Week 2 (± 3d)	Week 4 (± 5d)		Week 6 (± 5d)	Week 8 (± 5d)		Week 10 (± 5d)	Week 12 ^b (± 5d)	Week 30 ^b (± 10d)	Week 48 (± 5d)
		Pre	Post		Pre	Post		Pre	Post				
		X											
Informed Consent	X												
Inclusion/Exclusion Criteria	X												
Medical History	X	X ^a											
Demographics	X												
Concomitant Medications	X	X		X	X		X	X		X			X
Physical Exam ^c	X	X		X	X		X	X		X			X
Vital Signs	X	X		X	X		X	X		X			X
Height and Weight	X												
CBC with Differential	X			X			X			X			X
Chemistry and Liver Function ^d	X			X			X			X			X
Serology ^e	X												
12-lead ECG	X												
Urinalysis Routine ^f	X			X			X			X			X
Pregnancy Test ^g	X	X			X ^k			X ^l					
INO-4700 or placebo + EP ^h		X ^{i,j}			X ^{i,k}			X ^{j,l}					
Download EP Data ^m			X			X ^k			X ^l				
Adverse Events ⁿ	X	X	X	X	X	X	X	X	X	X	X	X	X
Immunology 1y (Whole blood) ^o	X	X					X			X			X
Immunology (Serum) ^p	X	X					X			X			X

a. Screening assessment occurs from -60 days to -1 day prior to Day 0. If screening occurs within 14 days prior to Day 0, then do not repeat medical history prior to dosing.

b. Follow-up phone call to collect AEs

c. Full physical examination at screening and Week 48 (or any other study discontinuation visit) only. Targeted physical exam at all other visits.

d. Includes Na, K, Cl, HCO₃ or CO₂, Ca, PO₄, glucose, BUN, Cr, AST and ALT.

e. MERS-CoV antibody (per PI discretion), HIV antibody or rapid test, HBsAg, HCV antibody.

f. Dipstick for glucose, protein, and hematuria. Microscopic examination should be performed if dipstick is abnormal.

g. Serum pregnancy test at screening. Urine pregnancy test at other visits.

h. INO-4700 or placebo is prepared by unblinded pharmacy personnel. All doses delivered via ID injection followed by EP.

i. For Study Groups A, B and F, one injection preferably over deltoid muscle at Day 0 and Week 4. For Study Groups E and I, two injections with each injection over a different deltoid or lateral quadriceps, preferably over the deltoid muscles, at Day 0 and Week 4.

j. For Study Groups C and G, one injection preferably over deltoid muscle at Day 0 and Week 8. For Study Groups D and H, two injections with each injection over a different deltoid or lateral quadriceps, preferably over the deltoid muscles, at Day 0 and Week 8.

- k. Complete only for Study Groups A, B, E, F and I.
- l. Complete for Study Groups C, D, G and H.
- m. Following administration of INO-4700 or placebo, EP data will be downloaded from the CELLECTRA™ 2000 device and provided to Inovio.
- n. Includes AEs from the time of consent and all injection site reactions that qualify as an AE. All AEs collected until study discharge.
- o. 4 x 8.0 mL (32 mL) whole blood in Cell Preparation Tubes (CPT) tubes per time point. Note: At the investigator's discretion, rather than collecting a sample at screening, 64 mL (8 x 8.0 mL whole blood in CPT tubes) may be collected prior to dosing on Day 0.
- p. 1 x 8 mL blood in 10 mL red top serum collection tube per time point. Note: Collect four aliquots of 1 mL each (total 4 mL) serum at each time point prior to 1st dose. At the investigator's discretion, rather than collecting a sample at screening, 2 x 8 mL blood in two (2) 10 mL red top serum collection tubes (for eight aliquots of 1 mL each) may be collected prior to dosing on Day 0.

Table 1-2 Part 2 Schedule of Assessments (Day 0 & Week 4 Optimal Regimen)

Tests and assessments	Screen ^a	Day 0		Week 2 (± 3d)	Week 4 (± 5d)		Week 6 (± 5d)	Week 8 ^b (± 5d)	Week 12 (± 5d)	Week 30 ^b (± 10d)	Week 48 (± 5d)		Week 50 ⁱ (± 5d)	Week 68 ⁱ (± 10d)
		Pre	Post		Pre	Post					Pre	Post		
Informed Consent	X													
Inclusion/Exclusion Criteria	X													
Medical history	X	X ^a												
Demographics	X													
Concomitant Medications	X	X		X	X	X					X		X	X
Physical Exam ^c	X	X		X	X	X					X		X	X
Vital Signs	X	X		X	X	X					X		X	X
Height and Weight	X													
CBC with differential	X			X		X					X		X	X
Chemistry and Liver Function ^d	X			X		X					X		X	X
Serology ^e	X													
12-lead ECG	X													
Urinalysis Routine ^f	X			X		X					X		X	X
Pregnancy Test ^g	X	X			X						X ⁱ			
INO-4700 or placebo + EP ^h		X			X						X ⁱ			
Download EP Data ^j			X			X						X ⁱ		
Adverse Events ^k	X	X	X	X	X	X	X	X	X	X	X ⁱ		X	X
Immunology (Whole blood) ^l	X	X					X		X		X		X	X
Immunology (Serum) ^m	X	X					X		X		X		X	X

a. Screening assessment occurs from -60 days to -1 day prior to Day 0. If screening occurs within 14 days prior to Day 0, then do not repeat medical history prior to dosing.

b. Follow-up phone call to collect AEs.

c. Full physical examination at screening and Week 48 (participants receiving only two doses) or Week 68 (participants receiving three doses), as well as any other study discontinuation visit. Targeted physical exam at all other visits.

d. Includes Na, K, Cl, HCO₃ or CO₂, Ca, PO₄, glucose, BUN, Cr, AST, and ALT.

e. MERS-CoV antibody (per PI discretion), HIV antibody or rapid test, HBsAg, HCV antibody.

f. Dipstick for glucose, protein, and hematuria. Microscopic examination should be performed if dipstick is abnormal.

g. Serum pregnancy test at screening. Urine pregnancy test prior to dosing at other visits.

h. INO-4700 or placebo is prepared by unblinded pharmacy personnel. All doses delivered via ID injection followed by EP.

i. Complete only for participants receiving a third dose of either INO-4700 or placebo (Part 2B).

j. Following administration of INO-4700 or placebo, EP data will be downloaded from the CELLECTRA™ 2000 device and provided to Inovio.

k. Includes AEs from the time of consent and all injection site reactions that qualify as an AE. All AEs collected until study discharge.

- l. 4 x 8.0 mL (32 mL) whole blood in Cell Preparation Tubes (CPT) tubes per time point. Note: At the investigator's discretion, rather than collecting a sample at screening, 64 mL (8 x 8.0 mL whole blood in CPT) may be collected prior to dosing on Day 0).
- m. 1 x 8 mL blood in 10 mL red top serum collection tube per time point. Note: Collect four aliquots of 1 mL each (total 4 mL) serum at each time point prior to 1st dose. At the investigator's discretion, rather than collecting a sample at screening, 2 x 8 mL blood in two (2) 10 mL red top serum collection tubes (for eight aliquots of 1 mL each) may be collected prior to dosing on Day 0).

Table 1-3 Part 2 Schedule of Assessments (Day 0 & Week 8 Optimal Regimen)

Tests and assessments	Screen ^a	Day 0		Week 2 (± 3d)	Week 4 ^b (± 5d)	Week 8 (± 5d)		Week 10 (± 5d)	Week 12 ^b (± 5d)	Week 30 ^b (± 10d)	Week 48 (± 5d)		Week 50 ⁱ (± 5d)	Week 68 ⁱ (± 10d)
		Pre	Post			Pre	Post				Pre	Post		
Informed Consent	X													
Inclusion/Exclusion Criteria	X													
Medical history	X	X ^a												
Demographics	X													
Concomitant Medications	X	X		X		X		X			X		X	X
Physical Exam ^c	X	X		X		X		X			X		X	X
Vital Signs	X	X		X		X		X			X		X	X
Height and Weight	X													
CBC with differential	X			X				X			X		X	X
Chemistry and Liver Function ^d	X			X				X			X		X	X
Serology ^e	X													
12-lead ECG	X													
Urinalysis Routine ^f	X			X				X			X		X	X
Pregnancy Test ^g	X	X				X					X ⁱ			
INO-4700 or placebo + EP ^h	X	X				X					X ⁱ			
Download EP Data ^j			X				X					X ⁱ		
Adverse Events ^k	X	X	X	X	X	X	X	X	X	X	X ⁱ	X	X	X
Immunology (Whole blood) ^l	X	X				X		X			X		X	X
Immunology (Serum) ^m	X	X				X		X			X		X	X

a. Screening assessment occurs from -60 days to -1 day prior to Day 0. If screening occurs within 14 days prior to Day 0, then do not repeat medical history prior to dosing.

b. Follow-up phone call to collect AEs.

c. Full physical examination at screening and Week 48 (participants receiving only two doses) or Week 68 (participants receiving three doses), as well as any other study discontinuation visit. Targeted physical exam at all other visits.

d. Includes Na, K, Cl, HCO₃ or CO₂, Ca, PO₄, glucose, BUN, Cr, AST and ALT.

e. MERS-CoV antibody (per PI discretion), HIV antibody or rapid test, HBsAg, HCV antibody.

f. Dipstick for glucose, protein, and hematuria. Microscopic examination should be performed if dipstick is abnormal.

g. Serum pregnancy test at screening. Urine pregnancy test prior to dosing at other visits.

h. INO-4700 or placebo is prepared by unblinded pharmacy personnel. All doses delivered via ID injection followed by EP.

i. Complete only for participants receiving a third dose of either INO-4700 or placebo (Part 2B).

j. Following administration of INO-4700 or placebo, EP data will be downloaded from the CELLECTRA™ 2000 device and provided to Inovio.

k. Includes AEs from the time of consent and all injection site reactions that qualify as an AE. All AEs collected until study discharge.

- l. 4 x 8.0 mL (32 mL) whole blood in 10 mL Cell Preparation Tubes (CPT) per time point. Note: At the investigators' discretion, rather than collecting a sample at screening, 64 mL (8 x 8.0 mL whole blood in CPT) may be collected prior to dosing on Day 0.
- m. 1 x 8 mL blood in 10 mL red top serum collection tube per time point. Note: Collect four aliquots of 1 mL each (total 4 mL) serum at each time point prior to 1st dose. At the investigator's discretion, rather than collecting a sample at screening, 2 x 8 mL blood in two (2) 10 mL red top serum collection tubes (for eight aliquots of 1 mL each) may be collected prior to dosing on Day 0.

1.2.5. Safety, Immunology, and Exploratory Parameters

1.2.5.1. Safety Parameters

- Incidence of adverse events (AEs) summarized by system organ class (SOC), preferred term (PT), and grouped by severity and relationship to investigational product.
- Frequency and severity of injection site reactions.
- Incidence of adverse events of special interest (AESIs).

Details and definitions of AEs are provided in the [Section 4.3.2.2](#).

1.2.5.2. Immunology Parameters

- Overall Immune Response
 - MERS-CoV antigen specific antibodies
 - Antigen-specific cytokine-producing T cell responses

1.2.5.3. Exploratory Parameters

The exploratory endpoint of expanded immune response parameters will include (provided there are available samples):

- Change in T and B cell immunologic proteins levels
- Change in levels of mRNA for genes of interest
- Antibodies to other coronaviruses

In addition to the overall immune response, endpoints to determine the response to the booster dose response for selected participants will be measured, including

- MERS-CoV antigen specific antibodies
- Antigen-specific cytokine-producing T cell responses
- T and B cell responses from immunogenicity assays

2. PARTICIPANT POPULATION

2.1. Population Definitions

The following participant populations will be used for presentation and analysis of the data:

- The modified intention to treat (mITT) population - includes all participants who receive at least one dose of the INO-4700 or placebo. Participants in this sample will be analyzed by their original assigned dose of INO-4700 or placebo. The mITT population will be used to analyze co-primary and exploratory immunological endpoints.
- The per-protocol (PP) population - comprises mITT participants who receive all their planned administrations and who have no Medical Monitor-assessed important protocol violations. Analyses on the PP population will be considered supportive of the corresponding mITT analyses. Participants excluded from the PP population will be identified and documented prior to locking the study database.
- The safety population (SP) - includes all participants who receive at least one dose of INO-4700 or placebo administered by ID injection. Participants for this population will be grouped in accordance with the dose of INO-4700 or placebo that they received. This population will be used for all safety analyses in the study.

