8.2 GENERAL CONSIDERATIONS

The statistical analysis of the data will be performed by Inovio Pharmaceuticals, or its representative. This is a randomized across Study Group, investigator-and-participant blinded, placebo-controlled (SSC-0001), multi-center phase 2a trial to evaluate the safety, tolerability and immunological profile of INO-4700 administered in healthy adult volunteers. Approximately 542 volunteers will be evaluated across two (2) parts: Part 1 Dose Finding and Part 2 Expansion.

Approximately 192 participants in Part 1 will be randomized across each group (A through I; see [Table 1](#)) to receive either INO-4700 or placebo. Upon completion of the Week 10 visit by all Part 1 participants including evaluable immunological data from all Study Groups, one optimal Study Group dose and regimen will be selected for expansion into Part 2. Participants in Part 1 will be followed until Week 48.

Approximately 350 participants in Part 2 will be randomized to receive the optimal dose of INO-4700 or placebo (see [Table 2](#)). The first 225 participants randomized in parallel to three Study Groups will receive a third dose of either INO-4700 or placebo at Week 48. Participants will either receive a week 48 active treatment administration on top of their two prior active treatment administrations (N=100), or a week 48 placebo administration on top of their two prior active treatment administrations (N=100) or a week 48 placebo administration on top of two prior placebo administrations (N=25). Collectively, these first 225 participants will be followed until Week 68. The remaining 125 participants will be randomized in parallel to either 2 active treatment administrations (N=100) or 2 placebo administrations (N=25) and followed until Week 48.

Details on the Study Group design and conduct and frequency of DMSB meetings can be found in [Sections 3.0](#) and [12.1](#).

The trial's primary analyses pertains to the evaluation of the tolerability, safety and overall immune response to INO-4700 administered by ID injection followed by EP in healthy volunteers. Exploratory analyses concern the evaluation of the expanded immunological response to INO-4700 delivered by ID injection followed by EP, the cellular (T cell) and humoral immune response to boosting with a third INO-4700 ID injection followed by EP and the evaluation of the cross reactivity of other coronavirus spike proteins to the humoral

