8.4 ANALYTICAL POPULATIONS

Analysis populations will be:

The modified intention to treat (mITT) population includes all participants who receive at least one dose of the INO-4700 or placebo. Participants in this sample will be analyzed by their original assigned dose of INO-4700 or placebo. The mITT population will be used to analyze co-primary and exploratory immunological endpoints.

The per-protocol (PP) population is comprised of mITT participants who receive all their planned administrations and who have no Medical Monitor-assessed important protocol violations. Analyses on the PP population will be considered supportive of the corresponding mITT analyses. Participants excluded from the PP population will be identified and documented prior to locking the study database.

The safety analysis population includes all participants who receive at least one dose of INO-4700 or placebo administered by ID injection. Participants for this population will be grouped in accordance with the dose of INO-4700 or placebo that they received. This population will be used for all safety analyses in the study.

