4.3. Immunology, Safety, and Exploratory Evaluations

4.3.1. Immunology Evaluations

The following immunogenicity analyses will be conducted on participants in the PP and mITT study populations.

In Part 1, the difference in percentage of overall immune responders including seroconverters (i.e. positive titer) between all pairs of INO-4700 study groups will be calculated along with corresponding exact (Clopper-Pearson) 95% CIs. The T and B cell immune responses to INO-4700 will be measured using assays that include ELISA, neutralization, assessment of immunological gene expression, assessment of immunological protein expression, flow cytometry, and ELISPOT.

In Part 2, the primary hypothesis of $H_0: p \leq 70\%$ versus $H_1: p > 70\%$ will be tested with an exact test of a binomial proportion. In addition, the binding antibody titer difference between INO-4700 and placebo will be analyzed using the geometric mean fold ratio and associated 95% confidence interval. Percent neutralizing antibodies and antigen specific cellular immune response differences between INO-4700 and placebo will be analyzed using the difference in medians and associated 95% CIs.

For both Part 1 and Part 2, antigen specific binding antibody titers, MERS-CoV neutralizing antibody titers, antibodies to other coronaviruses, and specific cellular immune responses will

be analyzed by study group and treatment group, respectively. Time to peak post-baseline titers will be summarized using descriptive statistics. Binding antibody titer will be analyzed for each study group using the geometric mean and associated 95% CIs. Percent neutralizing antibodies and antigen specific cellular immune response increases will be analyzed for each study group using medians, inter-quartile range and 95% CIs. Percentage with overall immune response, inclusive of seroconversion and corresponding 95% Clopper-Pearson CIs will be analyzed within each study and treatment group.

All immunologic data will be presented in data listings.

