5. CHANGES TO PLANNED ANALYSES

1. Updated analysis population to include Per Protocol (PP) for:
 - Demographics and Baseline Characteristics ([Section 4.2](#))
 - Concomitant Medication ([Section 4.3.2.6.](#))
2. Key analysis population has been changed to PP for Immunogenicity ([Section 4.3.1.](#)).

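### The Per-Protocol definition has no visit limit, so a missed Week 48 third dose removes a participant from the Part 2 two-dose response test as well

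*SAP*

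**What the plan says.** **Population.** SAP 2.1 says that PP "comprises mITT participants who receive all their planned administrations and who have no Medical Monitor-assessed important protocol violations". Protocol 8.4 has the same definition. Both add that "Participants excluded from the PP population will be identified and documented prior to locking the study database". Neither restricts the rule to particular doses, visits or endpoints.

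**Role of PP.** SAP 2.1 states: "Analyses on the PP population will be considered supportive of the corresponding mITT analyses". Protocol 8.4 agrees. SAP 5 states: "Key analysis population has been changed to PP for Immunogenicity". SAP 4.3.1 names both sets: "The following immunogenicity analyses will be conducted on participants in the PP and mITT study populations".

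**Doses planned in Part 2.** Protocol 8.2 states: "The first 225 participants randomized in parallel to three Study Groups will receive a third dose of either INO-4700 or placebo at Week 48". SAP 1.2.1 says of the active arm: "The first 200 participants from the Active treatment group will be randomized to receive either a booster dose or placebo at Week 48". SAP 1.2.2 has these 225 randomised to the booster regimens from the start, and the other 125 to two doses. The active arm is therefore 200 with three planned administrations and 100 with two.

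**The test.** Protocol 8.3 and SAP 4.3.1 set H0: p ≤ 70% against H1: p > 70%, by an exact binomial test. SAP 3.1 bases it on 260 evaluable actives at one-sided 0.025. No visit is named for the response.

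**The concern.** One hundred actives never receive a third dose and leave at Week 48. A test that pools all actives can therefore only concern the response to two doses. Yet for the other 200, membership of PP depends on an injection given long after that response was sampled.

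Take two participants with the same two doses and the same valid sample. One was randomised among the first 225 and misses Week 48 because of pregnancy, an adverse event or refusal. The other was randomised later. The first leaves PP and the second stays, and nothing about the two-dose response distinguishes them.

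Conditioning on a later event discards usable data. It also shifts the estimated rate if those who miss the third dose differ in response. How much this matters depends on whether PP is the key analysis, and the SAP contradicts itself on that.

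**Working it through.** **1. Gap between response and third dose.** Protocol 3.6 places the samples after dose 2 and before Week 48 at Weeks 6 and 12 (Week 4 regimen) or Week 10 (Week 8 regimen). The gaps are 48 − 6 = 42, 48 − 10 = 38 and 48 − 12 = 36 weeks. That the response is read at one of these visits is an inference from the schedule.

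**2. The plan's own power figure.** Inputs from SAP 3.1 are n = 260, rates 70% and 80%, and one-sided 0.025. The rule is the smallest r with P(X ≥ r | n, 0.70) ≤ 0.025. This gives r = 197 (197/260 = 75.8%), exact size 0.0232 and power P(X ≥ 197 | 260, 0.80) = 0.960. The stated >90% is reproduced.

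**3. Loss of numbers.** The documents give no rate of missed third doses, so the rates here are assumptions. With miss rate d and no other loss, PP actives number 100 + 200(1 − d).

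| d | PP actives | Cutoff r | Power at 80% |
|---|---|---|---|
| 0 | 300 | 226 | 0.980 |
| 10% | 280 | 212 | 0.967 |
| 20% | 260 | 197 | 0.960 |
| 40% | 220 | 168 | 0.922 |

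Adding early loss of 40/300 = 13.3%, the allowance implied by 260 of 300, and then d = 20% or 30% leaves 225 or 208, with power 0.920 or 0.912.

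**4. Selection.** Let the true two-dose rate be 70% in all 300, and let those who miss Week 48 respond at q. The expected PP rate is (0.70 × 300 − q × 200d) / (300 − 200d). The rejection chance is the binomial tail at that rate beyond the cutoff for the reduced n.

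| d | q | Expected PP rate | Cutoff | P(reject) |
|---|---|---|---|---|
| 10% | 60% | (210 − 12)/280 = 70.7% | 212/280 | 0.036 |
| 20% | 60% | (210 − 24)/260 = 71.5% | 197/260 | 0.073 |
| 20% | 50% | (210 − 20)/260 = 73.1% | 197/260 | 0.182 |

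With q = 70%, missing is unrelated to response and P(reject) returns to the exact size of the test: 0.0201 at n = 280 and 0.0232 at n = 260. With q above 70% the bias runs the other way and makes rejection less likely.

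**5. The Week 12 review.** Protocol 8.5.6 and SAP 3.12 provide group-level immunogenicity summaries after Week 12. No Week 48 dose is due by then, so any PP output produced there could not apply the full rule to the 225.

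**The case against.** The strongest reply is that PP may not matter much. SAP 2.1 and Protocol 8.4 both call it supportive and assign the immunogenicity endpoints to mITT. SAP 4.3.1 runs the same analyses in mITT, which drops nobody for a missed third dose. If those statements govern, the rule touches only a sensitivity analysis, and a divergence between the two runs would be visible. This stands as a limit on the consequences. It does not remove the point, because SAP 5 is the explicit record of a change and names PP as key.

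A reader might infer more than the documents support in four ways.

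- **Lost power.** A 20% miss rate alone removes 40 people, the whole margin between 300 and 260. But power at 260 is 0.960, and it stays above 90% in every scenario computed above.
- **A swing in the decision.** With a true rate of 75% and 40 dropped, PP would expect (225 − 24)/260 = 77.3% if they respond at 60%, or (225 − 36)/260 = 72.7% if at 90%. These straddle the 75.8% cutoff, but only because 75% lies next to it. With all 300 retained the test rejects only 48% of the time at 75%. At the plan's alternative of 80%, the same 15-point differences give (240 − 26)/260 = 82.3% or (240 − 38)/260 = 77.7%, both above the cutoff.
- **A known direction of bias.** Nothing in the documents links missing a third injection to immune response.
- **Different people at Week 12 and at the end.** That would follow only if a PP summary were produced at Week 12. No section specifically assigns one.

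**Conclusion.** The gap is in the text. One PP rule without a visit limit makes the two-dose test depend on a dose due 36 to 42 weeks later, and only for the 200 actives (and 25 placebos) given three-dose regimens. The consequences are moderate. Some precision is lost, and there is a possible selection bias that is zero when missing Week 48 is unrelated to response.

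With a true rate of 70%, 10–20% of the 200 missing Week 48 and a 60% response among them, false rejection is 0.036–0.073 instead of at most 0.025. Those three inputs are assumptions, and the response visit is inferred. The effect reaches the main conclusion only if SAP 5 prevails over SAP 2.1 and Protocol 8.4.

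A reader might also ask whether any reported result is affected. None is: the later administrative memo states that the trial will not proceed to Part 2. This is a flaw in the plan only.

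**What to change.** In SAP 2.1 and Protocol 8.4, define PP by analysis visit: mITT participants who received every administration planned before that visit and had no important violation up to it. Use the resulting two-dose PP for the Part 2 70% test and for any PP summary at Week 12. Require the third dose only for the Week 50 and Week 68 booster analyses. Name the visit at which the tested response is read.

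Separately, reconcile SAP 5 with SAP 2.1 and Protocol 8.4 by stating whether PP or mITT is primary for immunogenicity.

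The population rule costs one sentence in each document and one additional population flag; the visit and the primary population need a statement each. No new data are needed. With Part 2 cancelled, the change has no remaining use in this trial unless that part is revived or the wording is reused elsewhere.
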